## 9 Safety Analysis

Standard safety variables to be analyzed include AEs, clinical laboratory tests, vital signs, electrocardiograms (ECGs), and physical examination. In addition, data from the following safety scales will be evaluated: MMSE score, assessments of suicidality (e.g, Sheehan-STS), and extrapyramidal symptoms (EPS; e.g, the Simpson-Angus Scale, abnormal involuntary movement scale [AIMS], and Barnes Akathisia Rating Scale [BARS]). Safety analysis will be conducted based on the Safety Sample. In general, baseline of a safety variable is defined as the last observation of the variable before taking the first dose of IMP, unless specified otherwise. Prospectively defined criteria will be used to identify potentially clinically relevant (PCR) abnormal values for clinical laboratory tests, vital signs, ECGs, body weight, and BMI.

### 9.1 Adverse Events

All AEs will be coded by system organ class and Medical Dictionary for Regulatory Activities (MedDRA) preferred term. The incidence of the following events will be summarized by treatment group:

- Treatment-emergent AEs (TEAEs)
- TEAEs by severity
- TEAEs with an outcome of death
- Serious TEAEs
- TEAEs leading to discontinuation of the IMP

The above summaries will also be prepared for TEAEs potentially causally related to the IMP.

### 9.2 Clinical Laboratory Tests

#### 9.2.1 Change from Baseline in Lab Tests

Summary statistics for mean and mean change from baseline in the routine clinical laboratory measurements, prolactin concentrations, coagulation parameters (prothrombin time, activated partial thromboplastin time, and international normalized ratio), HbA1c, and thyroid-stimulating hormone will be provided by treatment and by visit.

#### 9.2.2 Potentially Clinically Relevant Values

In addition, the incidence of treatment-emergent PCR values identified using prospectively defined criteria in [Appendix 1](#) for laboratory tests will be summarized by treatment group. A listing of PCRs by subject and by test will be provided.

### 9.2.3 Potentially Liver Injury Related Laboratory Test

Total bilirubin level will be checked for any subjects with increased alanine transaminase (ALT) or aspartate transaminase (AST) levels greater or equal to three times the upper normal limits (or baseline).

Liver injury related laboratory test results will be summarized for subjects who met following criteria in the Short-term Controlled Trials and Long-term Open-label Trials groups. The corresponding listing will be provided as well.

- AST or ALT  $\geq 3 \times$  upper limit of normal (ULN) and
- T\_Bili  $\geq 2 \times$  ULN

### 9.2.4 Metabolic Change

In addition to mean change from baseline, the incidence of treatment emergent significant changes in fasting lipids, fasting glucose, and metabolic syndrome will be summarized by treatment group using the following criteria.

Table 9.2.4-1 Criteria for Treatment-Emergent Significant Change in Lipids and Glucose		
Lab Parameter	Baseline a	Anytime Post Baseline
LDL Direct, Fasting (mg/dL)	Borderline 100 < 160 Normal/Borderline < 160 Normal < 100 Any Value	High $\geq 160$ High $\geq 160$ Borderline/High $\geq 100$ Increased $\geq 30$
HDL Cholesterol, Fasting (mg/dL)	Normal $\geq 40$ Any Value	Low $< 40$ Decreased $\geq 20$
Triglycerides, Fasting (mg/dL)	Normal < 150 Borderline 150 < 200 Normal/Borderline < 200 Normal < 150 Any Value	High 200 < 500 High 200 < 500 High 200 < 500 Borderline/High/Very High $\geq 150$ Increased $\geq 50$
Glucose Fasting, Serum(mg/dL)	Normal < 100 Impaired 100 < 126 Normal/Impaired < 126 Any Value	High $\geq 126$ High $\geq 126$ High $\geq 126$ Increased $\geq 10$

a Baseline is calculated from Day 0; if Day 0 is unavailable screen visit will be used

Table 9.2.4-2 Criteria for Treatment-Emergent Metabolic Syndrome		
Description	Lab Parameter	Anytime Post Baselinea
Central Obesity	Waist Circumference	Males: $\geq 102$ cm Females: $\geq 88$ cm
Dyslipidemia	Triglycerides	$\geq 150$ mg/dL
	HDL	Males: $< 40$ mg/dL Females: $< 50$ mg/dL
Supine Blood Pressure	Systolic	$\geq 130$ mmHg
	Diastolic	$\geq 85$ mmHg
Fasting Glucose	Glucose Fasting, Serum	$\geq 100$ mg/dL

a Baseline is calculated from Day 0; if Day 0 is unavailable screen visit will be used

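### In SAP Table 9.2.4-1 the triglyceride High rows stop below 500 mg/dL, so a shift from Borderline to 500 or more has no category-shift row

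*SAP*

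**What the plan says.** SAP Section 9.2.4 states that "the incidence of treatment emergent significant changes in fasting lipids, fasting glucose, and metabolic syndrome will be summarized by treatment group", using the criteria in its two tables. For triglycerides, Table 9.2.4-1 lists five baseline entries, "Normal < 150 Borderline 150 < 200 Normal/Borderline < 200 Normal < 150 Any Value". The first three are paired with the destinations "High 200 < 500 High 200 < 500 High 200 < 500" and the last two with "Borderline/High/Very High $\geq 150$ Increased $\geq 50". The destination column is headed "Anytime Post Baseline", so any qualifying post-baseline value is enough.

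Two other analytes in the same table are set up differently. The LDL destinations are "High $\geq 160$ High $\geq 160$ Borderline/High $\geq 100$ Increased $\geq 30" and the fasting glucose destinations are "High $\geq 126$ High $\geq 126$ High $\geq 126$ Increased $\geq 10". None of these has an upper limit.

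Elsewhere, SAP Appendix 1 flags fasting triglycerides of 150 mg/dL or more, and Table 9.2.4-2 uses the same threshold for metabolic syndrome. Neither is capped.

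**The concern.** The table names a Very High tier for triglycerides and ends High where that tier begins, but gives Very High no row of its own. It appears only inside a composite destination that is open to Normal baselines alone. The count is therefore not monotone: a larger rise can leave a category that a smaller rise enters. For a Borderline baseline, no category row catches the larger rise.

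What is at stake is the by-arm incidence of worsening in lipid category, a descriptive safety output. The rows labelled High can miss a subject whose triglycerides went beyond High, and a reader of the table would not expect that.

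**Working it through.** No sample-size, power or alpha figure is involved, so there is no plan figure to reproduce. The check applies the five rows as printed.

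**Inputs (SAP Table 9.2.4-1, mg/dL).** An entry of the form a < b is read as a ≤ value < b. This is how the Borderline band must be read for it to adjoin Normal (below 150) without a gap. With B for baseline and V for any post-baseline fasting value:

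1. Normal to High: B < 150 and 200 ≤ V < 500
2. Borderline to High: 150 ≤ B < 200 and 200 ≤ V < 500
3. Normal/Borderline to High: B < 200 and 200 ≤ V < 500
4. Normal to Borderline/High/Very High (composite): B < 150 and V ≥ 150
5. Any value, increased: V − B ≥ 50

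**Which rows can apply.** A Normal baseline can enter rows 1, 3, 4 and 5, which is four rows; row 2 is closed to it at every post-baseline value. A Borderline baseline can enter rows 2, 3 and 5.

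**What happens at V ≥ 500.** Rows 1 to 3 all require V < 500 and fail. Row 4 holds only if B < 150. Row 5 always holds for B < 200, because V − B > 500 − 200 = 300 ≥ 50.

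**Worked cases.**

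| Baseline | Post-baseline value(s) | Rows met as written | Rows met if rows 1 to 3 used V ≥ 200 |
|---|---|---|---|
| 140 | 499 | 1, 3, 4, 5 | 1, 3, 4, 5 |
| 140 | 500 | 4, 5 | 1, 3, 4, 5 |
| 140 | 300 and 550 | 1, 3, 4, 5 | 1, 3, 4, 5 |
| 180 | 499 | 2, 3, 5 | 2, 3, 5 |
| 180 | 500 | 5 | 2, 3, 5 |
| 180 | 520 and 550 | 5 | 2, 3, 5 |
| 180 | 300 and 550 | 2, 3, 5 | 2, 3, 5 |

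A grid of whole-number baselines from 30 to 199 against a single post-baseline value from 500 to 1500 gave no combination in rows 1 to 3. With the baseline restricted to 150 to 199, none fell in rows 1 to 4.

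**Result.** Between 499 and 500, a Normal baseline loses two of its four applicable rows (1 and 3) and keeps the composite and increase rows. A Borderline baseline loses both of its category-shift rows and keeps only the increase row. A second value from 200 to below 500 restores the full count in either case.

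**How often a second value exists.** The Schedule of Assessments (Protocol Table 3.7-1) places post-baseline serum chemistry at Week 8 and at Week 12 or early termination. Protocol Section 3.7.5.2 requires an 8-hour fast at Week 12 or early termination but asks for it only if possible at Week 8. Scheduled sampling therefore gives at most two fasting values, and some subjects will have one.

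**The case against.** The case for leaving the table alone has four parts.

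- Keeping High separate from Very High is legitimate, and a bounded High band is not an error in itself. This stands. The fault is the missing Very High destination, not the bound.
- The any-time rule counts a subject who passes through 200 to below 500 at another visit. This stands for those subjects. With at most two scheduled fasting values, it is only a partial safeguard.
- Every subject who goes from below 200 to 500 or more remains in the row for increases of 50 or more. This also stands. That row, however, puts a rise from 90 to 140 together with one from 180 to 550, so it cannot show a change of category.
- Such a value meets the uncapped threshold of 150 in Appendix 1, which Section 9.2.2 summarises by treatment group and lists by subject, and it meets the same threshold in Table 9.2.4-2. This stands as well: the value itself is not lost. But those counts do not distinguish 151 from 550, and a Borderline subject is already at 150 or more at baseline. If treatment-emergent means newly met after baseline, that subject might not be counted as emergent there. Section 9 of the SAP does not define the term for laboratory values.

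SAP Addendum 2 does not alter the point. It says that methods and conventions are unchanged. The text of its updated list of summary tables was not available, so nothing is claimed about that list.

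**Conclusion.** The gap is real and minor. Followed exactly, Table 9.2.4-1 has no category-shift row for a Borderline baseline when the only post-baseline fasting values at or above 200 are 500 or more. For a Normal baseline in the same position, two of four applicable rows are missed.

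A reader might infer more than this, and the documents do not support it:

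- That such a subject vanishes from the table. Not so: the increase row always counts the subject, and the composite row counts those with a Normal baseline.
- That a Normal-baseline subject is missed in three of the five rows. One of those three, Borderline to High, never applied to that subject.
- That the safety signal is understated where it is largest. Nothing in the documents shows how many subjects reach 500 or more, or that a comparison between arms would change. The same definition applies to both arms.

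The number affected cannot be stated and is probably small. The output is descriptive, so no efficacy result, alpha allocation or power figure depends on it. The conclusion assumes that the printed bounds are the intended ones; the repeated cap and the separately named Very High tier make a misprint unlikely.

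**What to change.** Add destination rows for Very High, 500 mg/dL or more, from the Normal, Borderline and Normal/Borderline baselines. This keeps the table's own distinction between High and Very High and gives the top tier its own incidence. It also matches SAP Table 9.4-1, where QTc above 500 msec has a separate row.

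Alternatively, relabel the three existing rows High/Very High with a criterion of 200 or more. The last column of the worked cases shows that this restores the missing counts, at the price of merging the two tiers.

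Either change needs an edit to the table shell and its programming, and no new data.

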### 9.3 Physical and Neurological Examination and Vital Signs

Physical and neurological examination findings will be listed by subject.

Summary statistics for change from baseline in vital signs, body weight, and waist circumference will be provided by treatment group.

In addition, the incidence of treatment-emergent PCR values identified using prospectively defined criteria in [Appendix 2](#) for vital signs and body weight will be summarized by treatment group. Listing of PCRs by subject and by test will be provided.

### 9.4 12-Lead ECG

Summary statistics for change from baseline in ECG parameters will be provided by treatment and by visit.

In addition, the incidence of treatment-emergent PCR values identified using prospectively defined criteria for ECG will be summarized by treatment group. Listing of PCRs by subject and by test will be provided.

For the analysis of QT and QTc, data from three consecutive complexes (representing three consecutive heart beats) will be measured to determine average values. The following QT corrections will be used for reporting purposes in the clinical study report:

- QTcB is the length of the QT interval corrected for heart rate by the Bazett formula:  $QTcB = QT / (RR)^{0.5}$
- QTcF is the length of the QT interval corrected for heart rate by the Fridericia formula:  $QTcF = QT / (RR)^{0.33}$
- QTcN is the length of the QT interval corrected for heart rate by the FDA Neuropharm Division formula:  $QTcN = QT / (RR)^{0.37}$

Categorical changes in ECG parameters during the double-blind treatment period will be summarized based on the criteria in [Table 9.4-1](#).

Table 9.4-1 Categorical Change Criteria in QT/QTc Parameters		
Classification	Category	Criteria
QT	New onset ( $\geq 450$ msec for men or $\geq 470$ msec for women)	New onset in QT means a subject who attains a cut off value during treatment period but not at baseline.
QTc a	New onset ( $\geq 450$ msec for men or $\geq 470$ msec for women)	New onset in QTc means a subject who attains a cut-off value during treatment period but not at baseline.
	New onset ( $\geq 450$ msec for men or $\geq 470$ msec for women) and $> 10\%$ increase	New onset and $> 10\%$ increase in QTc means a subject who attains a cut off value and $> 10\%$ increase during treatment period but not at baseline
	New onset ( $> 500$ msec)	New onset ( $> 500$ msec) in QTc means a subject who attains a value $> 500$ msec during treatment period but not at baseline.
	Increase 30 - 60 msec	Increase from baseline value $> 30$ and $\leq 60$ msec in QTc
	Increase $> 60$ msec	Increase from baseline value $> 60$ msec in QTc

a QTc categorical change criteria apply to QTcB, QTcF and QTcN.

## 9.5 Body Weight, Waist Circumference and Body Mass Index

Analyses of body weight, waist circumference and BMI will be performed for the Safety Sample. Body mass index is defined as weight in kilograms divided by the square of height in meters. The mean change from baseline to Week 12 and the last visit in the double-blind treatment period in body weight will be tabulated and analyzed using analysis of covariance (ANCOVA). The ANCOVA models will include the baseline as a covariate and the treatment group as fixed effect.

Percentages of subjects showing significant weight gain ( $\geq 7\%$  increase in weight), as well as percentages of subjects showing significant weight loss ( $\geq 7\%$  decrease in weight) from baseline to Week 12 (OC and LOCF) will be analyzed using CMH General Association Test.

## 9.6 Simpson-Angus Scale, Abnormal Involuntary Movement Scale, and Barnes Akathisia Rating Scale

The mean change from baseline to Week 12/ET in the double-blind treatment period obtained from the Simpson-Angus Scale total score, AIMS total score (total of the first 7 item scores), and BARS Global Clinical Assessment will be performed for the Safety Sample and tabulated and analyzed using ANCOVA.

The ANCOVA model will include the baseline measure and the treatment group.

The same analyses will be performed on the AIMS individual item scores 8, 9, and 10. In addition, incidence of BARS Global Clinical Assessment of Akathisia during the double-blind treatment period by severity category will be provided. Analyses of these EPS rating scales will be performed for the Safety Sample.

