Assessment	Screening ^a	Baseline (Day 0)	Week 2 (±2 days)	Week 4 (±2 days)	Week 6 (±2 days)	Week 8 (±2 days)	Week 10 (±2 days)	Week 12 or ET ^b (±2 days)	Follow- up ^c (+2 days)	Week 16 ^d	Notes
Prolactin (blinded)	X							X			Section 3.7.5.2
TSH with reflex to free T ₄ if abnormal	X										Section 3.7.5.2
HbA _{1c}	X							X			Section 3.7.5.2
PT, aPTT, and INR	X							İ			Section 3.7.5.2
Urine pregnancy test (women of childbearing potential) only	X							X			Section 3.7.5.2
ECG	X	X				X		X			Section 3.7.5.4
Urine drug screen and blood alcohol test	X										Section 3.7.5.2 Section 4.2
MMSE	X	X						X			
Sheehan-STS	X	X						X			Section 3.7.5.5.4
Extrapyramidal symptoms scales (SAS, AIMS, BARS)		X						X			
Adverse events	X	X	X	X	X	X	X	X	X		Section 5
Pharmacokinetic sampling		X				X		X			Section 3.7.6.1.1
			I	I			I				
Concomitant medications	X	X	X	X	X	X	X	X	X		Section 3.7.4
Mortality status assessment										X	Section 3.7.1.5
OTHER PROCEDURES											
IMP dispensing		X	X	X	X	X	X				Section 8.4
IMP accountability		X	X	X	X	X	X	X			

aPTT = activated partial thromboplastin time; INR = International Normalized Ratio; PT = prothrombin time.

^aSee Section 3.7.1.1.

^bSee Section 3.1.

^cSee Section 3.8.3.2.

^dNote that this visit is 16 weeks postbaseline and only for subjects who terminate early from the trial.

^eIf a previous MRI or CT scan of the brain performed after the onset of symptoms of dementia is not available, then an MRI/CT scan of the brain should be performed during screening. In addition, a repeat MRI/CT scan of the brain may be requested to be performed by CST or the IAP in order to confirm eligibility.

^fIf a fasting blood sample was obtained at the screening visit and less than 14 days have elapsed since the screening visit, clinical laboratory tests (hematology, serum chemistry, and urinalysis) do not need to be repeated at the baseline visit.

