3.7.5.5.3 Barnes Akathisia Rating Scale

The BARS²⁹ consists of 4 items related to akathisia: objective observation of akathisia by the investigator, subjective feelings of restlessness by the subject, subjective distress due to akathisia, and global clinical assessment of akathisia. The first 3 items will be rated on a 4-point scale, with a score of zero representing absence of symptoms and a score of 3 representing a severe condition. The global clinical evaluation will be made on a 6-point scale, with zero representing absence of symptoms and a score of 5 representing severe akathisia. To complete this scale, subjects will be observed while they are seated and then standing for a minimum of 2 minutes in each position. Symptoms observed in other situations (eg, while engaged in neutral conversation or engaged in other activity) may also be rated. Subjective phenomena are to be elicited by direct questioning. Propranolol is not permitted within 12 hours of scale administration (see Section 4.1). Investigators are encouraged to delay scale administration until the required time frame has elapsed, if at all possible. However, if delaying administration of the scale is not feasible, the BARS should still be administered and the use of the medication documented, including a notation of the drug name, dose, and time of administration on

the eSource. The BARS global score is defined as the global clinical assessment of akathisia.

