Table 4.1-1 List of Restricted and Prohibited Medications All other psychotropic agents not listed in the below table are prohibited and must be discontinued at least 24 hours before the first dose of IMP. **During Double-Blind Treatment** Medication Prior to Randomization Period Benzodiazepines Allowed but limited to During the first 4 weeks of the 6. (short-acting)a 4 days/week between screening randomized period (baseline to and randomization with a Week 4 visit): allowed but limited maximum dose of 2 mg/day of to 4 days/week with a maximum dose of 2 mg/day of lorazepam (or lorazepam (or equivalent) or less depending on dose-limiting equivalent) depending on doseside effects. limiting side effects. Prohibited after the Week 4 visit. Non-benzodiazepine sleep If a bedtime dose of a sleep If a bedtime dose of a sleep agent agents^b agent for insomnia was taken for insomnia was taken prior to prior to randomization on a randomization on a regular basis, regular basis, a stable pretrial a stable pretrial dose of the sleep agent may be continued as needed dose of the sleep agent may be continued as needed during the during the trial. If a sleep agent trial. If a sleep agent was not was not previously taken prior to randomization and needs to be previously taken prior to randomization and needs to be initiated, medication should be initiated, medication should be limited to a maximum dose of limited to a maximum dose of 5 mg/day of zolpidem (or 5 mg/day of zolpidem (or equivalent). equivalent). 8. Opioid analgesics Prohibited unless permission is Prohibited unless permission is obtained from the medical obtained from the medical monitor. Permission for opioid monitor. Permission for opioid use may be considered for a use may be considered for a documented and clinically documented and clinically appropriate indication (eg, appropriate indication (eg, episodic pain condition, tooth episodic pain condition, tooth extraction) if prescribed at a extraction) if prescribed at a medically appropriate dose and medically appropriate dose and frequency. frequency. 9. Anticholinergies for 7-day washout Prohibited treatment of extrapyramidal symptoms^c 10. Propranolol^d For treatment of akathisia or For treatment of akathisia or tremor: 7-day washout tremor: maximum dose of 20 mg. For treatment of heart disease: 3 times daily (total of 60 mg/day). For treatment of heart disease: allowed provided that the dose has been stable for 30 days may remain on stable pretrial prior to randomization and total doses as needed throughout the dose does not exceed trial, as long as the total dose does not exceed 60 mg/day. 60 mg/day Propranolol must not be administered within 12 hours prior to the efficacy and safety scales.

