### **10.3.8 Barnes Akathisia Rating Scale**

BARS will be used to assess the presence and severity of akathisia. This scale consists of 4 items. Only the 4th item, the Global Clinical Assessment of Akathisia, will be evaluated in this trial. This item is rated on a 6-point scale, with 0 being best (absent) and 5 being worst (severe akathisia).

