## 2 Addition of List of EPS-related AEs

[figure not shown]
EPS-related AEs are listed below and will be grouped into five categories.

[figure not shown]
- 1) Dystonic Events, which include blepharospasm, cervical spasm, clumsiness, dystonia, dystonic tremor, emprosthotonus, essential tremor, facial spasm, fumbling, gait inability, head titubation, intention tremor, Meige's syndrome, muscle contractions involuntary, muscle spasms, muscle spasticity, muscle tightness, muscle tone disorder, musculoskeletal stiffness, myotonia, nuchal rigidity, oculogyration, oesophageal spasm, opisthotonus, opisthotonus, oromandibular dystonia, oropharyngeal spasm, pharyngeal dystonia, pleurothotonus, risus sardonicus, spasmodic dysphonia, tongue spasm, torticollis, torticollis psychogenic, trismus, uvular spasm;
- 2) Parkinsonian Events, which include action tremor, akinesia, asterixis, bradykinesia, bradyphrenia, cogwheel rigidity, dysphonia, fine motor skill dysfunction, freezing phenomenon, gait disturbance, gait festinating, hypertonia, hypokinetic dysarthria, laryngeal tremor, masked facies, micrographia, mobility decreased, muscle rigidity, on and off phenomenon, parkinsonian crisis, parkinsonian gait, parkinsonian rest tremor, parkinsonism, parkinsonism hyperpyrexia syndrome, parkinsons disease, parkinson's disease, parkinson's disease psychosis, postural reflex impairment, postural tremor, propulsive gait, reduced facial expression, resting tremor, tremor, walking disability;
- 3) Akathisia Events, which include akathisia, extrapyramidal disorder, hyperkinesia, movement disorder, psychomotor hyperactivity, and restlessness;
- 4) Dyskinetic Events, which include abnormal involuntary movement scale, athetosis, ballismus, buccoglossal syndrome, chorea, choreoathetosis, chronic tic disorder, complex tic, dopamine dysregulation syndrome, drooling, dyskinesia, dyskinesia oesophageal, grimacing, motor dysfunction, muscle twitching, nodding of head, oculogyric crisis,

[figure not shown]
pharyngeal dyskinesia, protrusion tongue, provisional tic disorder, rabbit syndrome, respiratory dyskinesia, secondary tic, tardive dyskinesia, tic;

[figure not shown]
5) Residual Events, which include huntingtons disease and myoclonus.

[figure not shown]

[figure not shown]

[figure not shown]

[figure not shown]

This page is a manifestation of an electronically captured signature

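### SAP 9.6 calls the BARS akathisia table an incidence over the double-blind period, but one post-baseline rating gives only a point prevalence at Week 12/ET

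*SAP*

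**What the plan says.** SAP 9.6 plans two BARS outputs. The first is an ANCOVA of "The mean change from baseline to Week 12/ET in the double-blind treatment period". The second is a table: "incidence of BARS Global Clinical Assessment of Akathisia during the double-blind treatment period by severity category will be provided". SAP 10.3.8 limits both to one item: "Only the 4th item, the Global Clinical Assessment of Akathisia, will be evaluated in this trial", rated 0 to 5.

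In Protocol Table 3.7-1 the row that begins "Extrapyramidal symptoms scales (SAS, AIMS, BARS" is marked at baseline and at Week 12/ET. It is blank at screening and at Weeks 2, 4, 6, 8 and 10.

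Protocol Table 4.1-1 requires a 7-day washout of propranolol used for akathisia or tremor before randomization, and permits that use, with a dose cap, during double-blind treatment. Propranolol is barred within 12 hours of a rating, but Protocol 3.7.5.5.3 adds that "if delaying administration of the scale is not feasible, the BARS should still be administered and the use of the medication documented".

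SAP Addendum 2, Section 2, covers the adverse event side: "EPS-related AEs are listed below and will be grouped into five categories". One category is akathisia events.

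**The concern.** Incidence over a treatment period means the share of subjects affected at any time in it, or newly affected in it. A single rating at the end shows only who is affected then. SAP 9.6 does not define incidence, name the rating used, set a worst-value rule or deal with subjects who already have akathisia at baseline.

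Safety and tolerability are the trial's secondary objective. Two of every three subjects in the active arm are assigned 3 mg/day, while Protocol 1.3 describes the two completed trials in this population as supporting doses up to 2 mg/day. The akathisia events category in Addendum 2 also includes restlessness and psychomotor hyperactivity. Because restlessness is itself an agitation behaviour on the CMAI, a reader may treat BARS as the more specific measure. A BARS table read as 12-week incidence could then carry a statement about akathisia that these data cannot support.

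**Working it through.** The plan states no number on this point, so there is none to reproduce. The check sets the passages side by side and then uses assumed inputs to see whether the direction of error can be settled.

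**1. Ratings available.** Table 3.7-1 marks two of the eight columns from screening to Week 12/ET. Scheduled post-baseline ratings per subject: 2 − 1 = 1. The documents describe no unscheduled BARS rating.

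**2. No look-back.** Protocol 3.7.5.5.3 describes observation while seated and standing plus direct questioning, with no recall interval. The Sheehan-STS is also rated at baseline and Week 12/ET, but its post-screening form covers the time since the last visit (Protocol 3.7.5.5.4). That supports the incidence statement in SAP 9.8. BARS has nothing equivalent.

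**3. What one rating measures.** Among rated subjects, let P be the share at or above a given severity at Week 12/ET, and E the share ever at or above it on treatment. Then P ≤ E. They are equal only if no episode resolved, eased or was suppressed before the rating.

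**4. Propranolol.** Baseline is rated after washout of propranolol used for akathisia or tremor. The end rating may be taken on it. This can only lower P relative to E.

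**5. Baseline akathisia.** If incidence means new onset, subjects affected at baseline should not count. SAP 9.6 does not remove them, whereas SAP Table 9.4-1 defines each new-onset QT category as reached on treatment but not at baseline. This can push the figure above true new onset.

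**6. Can the direction be settled?** The documents give no akathisia rate, onset pattern, episode length or baseline BARS prevalence, so the inputs here are assumptions. Suppose each new episode starts at time s and lasts an exponentially distributed time with mean m weeks. The fraction r of new episodes still present at Week 12 is:

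- onset uniform over 12 weeks: r = (m/12)(1 − exp(−12/m))
- onset uniform over Weeks 0–4: r = (m/4)(exp(−8/m) − exp(−12/m))

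| Mean duration m (weeks) | r, onset over 12 weeks | r, onset in Weeks 0–4 | Shown if true incidence is 5% (onset over 12 weeks) |
|---|---|---|---|
| 2 | 17% | 1% | 0.8% |
| 4 | 32% | 9% | 1.6% |
| 8 | 52% | 29% | 2.6% |
| 12 | 63% | 44% | 3.2% |
| 26 | 80% | 68% | 4.0% |

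The shortfall in the m = 4 row is 5% × (1 − 0.317) = 3.4 percentage points. If a further 3.4% of subjects had akathisia at baseline that persisted to Week 12, the reported figure would equal the true incidence. With more than that it would exceed it. The sign depends on quantities the documents do not give.

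**The case against.** The strongest reply is that this is loose wording in a supplementary table. SAP 9.6 applies the same phrase about the double-blind period to a mean change that is plainly at Week 12/ET, so the phrase may only name the trial period, and the schedule shows the visit. The table lists in SAP Section 12 and Addendum 2 Section 3 were not in the text available for this review, so the table's title may already name the visit. The protocol itself evaluates BARS by mean change only (Section 3.5.4).

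There are also safeguards. Subjects who cannot tolerate their assigned dose are withdrawn and are to have the ET evaluations at that time, so akathisia that leads to withdrawal should be rated while present. The 12-hour rule reduces masking by propranolol, and exceptions must be documented.

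Most important, akathisia incidence is not lost. Adverse events are collected at every visit through follow-up, SAP 9.1 summarizes their incidence by treatment group, and Addendum 2 defines the akathisia category.

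Most of this stands, and it limits the point to labelling. It does not remove it: the sentence in SAP 9.6 still promises a quantity that one rating cannot give. The early termination visit does not catch akathisia that resolves, or is controlled with propranolol, in subjects who stay on treatment.

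A reader might go further and infer that the plan under-reports akathisia, or that the comparison between arms is biased toward no difference. The documents support neither. Understatement is possible but not shown, unexcluded baseline akathisia works the other way, and nothing says that transient or treated akathisia is commoner in one arm.

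**Conclusion.** The point holds as a labelling fault. The BARS output described as incidence over the double-blind period is a point prevalence at Week 12/ET. It rests on three facts in the documents: one scheduled post-baseline rating, no recall period in the scale as described, and permitted propranolol use before that rating. As a measure of subjects ever affected, the figure is a lower bound. As a measure of new onset, it may err in either direction. The size cannot be computed; the percentages in the table above follow from assumed onset and duration and are not estimates for this trial. The fault is confined to one secondary safety output. Efficacy, alpha and power are untouched, and the adverse event data still give akathisia incidence over the period.

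**What to change.** In SAP 9.6, replace the incidence wording with: *distribution of the BARS global score by severity category at Week 12/ET, presented as a shift from baseline*. The shift separates akathisia already present from akathisia that is new.

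Beside it, show the number of subjects in each arm with on-treatment propranolol use for akathisia or tremor, taken from the concomitant medication data already recorded under Protocol 3.7.4. This needs the reason for use, since propranolol is also allowed for heart disease. The documents do not say outright that the reason is captured; if it is not, counting subjects who start propranolol after the first dose is a workable substitute.

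Add one sentence stating that akathisia incidence over the period is taken from the planned treatment-emergent adverse event summaries, using the akathisia events category of Addendum 2.

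The cost is SAP wording and a little more table work, with no new ratings or visits. The resulting statement about akathisia may be less favourable than one read from the table as now described.
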